### 1.2. Trial Design

This is a randomized, open-label, active-controlled, multicenter study designed to assess the efficacy and safety of trabectedin + DOXIL as a third-line chemotherapy in subjects with platinum-sensitive advanced-relapsed epithelial ovarian, primary peritoneal, or fallopian tube cancer who received 2 previous lines of platinum-based chemotherapy. Approximately 670 subjects will be enrolled in this study, with 335 subjects per planned treatment group. At randomization, subjects will be stratified by the time from the last dose of first-line platinum therapy to disease progression (6 months to 12 months vs >12 months to 24 months vs >24 months), Eastern Cooperative Oncology Group (ECOG) performance status score (0 vs 1), BRCA 1/2 status (mutation vs no mutation), and prior pegylated liposomal doxorubicin therapy (no vs yes). Then they will be randomly assigned in a 1:1 ratio to the trabectedin + DOXIL combination therapy group (Arm A) or to the DOXIL monotherapy group (Arm B). Study treatment will be

YONDELIS®: Statistical Analysis Plan Study ET743-OVC-3006

administered by IV infusion on Day 1 of a 21-day cycle in Arm A and on Day 1 of a 28-day cycle in Arm B.

- **Treatment Arm A:** DOXIL 30 mg/m^2 90-minute IV infusion (per DOXIL package insert) followed by trabectedin 1.1 mg/m^2 3-h IV infusion, via central venous catheter, every 3 weeks. Central venous access is required for the administration of trabectedin.
- **Treatment Arm B:** DOXIL 50 mg/m^2 as a 90-minute IV infusion (per DOXIL package insert) every 4 weeks. If no infusion-related reaction is observed with DOXIL after the first infusion, DOXIL may be administered as a 30- to 90-minute infusion in subsequent cycles, as indicated in the product's Package insert.

Subjects assigned to the trabectedin + DOXIL group (Arm A) will be pretreated with 20 mg of dexamethasone (or an equivalent corticosteroid) 30 minutes prior to initiation of infusion of DOXIL IV, on Day 1 of each treatment cycle.

On 26 June 2017, the IDMC requested a futility analysis of OS to be performed at the time of the next meeting 6 months later. In view of the IDMC request, study data up to 20 September 2017 were evaluated for safety and OS (45% rather than 60% of the required death events at the planned interim analysis). Following the review of the study data by the IDMC on 15 December 2017, the HR for OS was 0.962, crossing the previously agreed upon threshold for futility of 0.93. In view of this result and the observed and expected higher toxicity in Arm A as compared with Arm B, the IDMC recommended discontinuing the study. Therefore, as of Amendment 6, no new subjects would be randomized to study treatment, and treatment with trabectedin should be immediately discontinued for subjects assigned to Arm A (trabectedin + DOXIL). All study subjects (Arm A or Arm B) currently on study treatment who, in the opinion of the investigator, were deriving clinical benefit may continue treatment with single-agent DOXIL as per the local standard of care. Treatment for these subjects may continue as long as the subjects comply with protocol-specified prohibitions and restrictions for treatment (Protocol Section 4.3) and as long as they experience clinical benefit in the opinion of the investigator. DOXIL would be provided by JR&D as needed until post-trial access to DOXIL is available or until disease progression, whichever occurs first.

Accordingly, the end of study data collection was defined as when all subjects on study treatment have completed treatment termination visit assessments as specified in the Time and Events Schedule for Amendment 6 or by 18 January 2018, whichever occurs first. For subjects continuing treatment with single-agent DOXIL, as per the local standard of care, only serious adverse events should be reported to JR&D.

### 1.3. Sample Size Justification

It is assumed that failure will follow an exponential distribution with a constant hazard rate. Assuming a median OS of 16 months for the active control group (DOXIL monotherapy), a planned sample size of approximately 670 subjects will provide 80% power to detect a HR of 0.78 (16 months versus 20.5 months; corresponding to a 28% improvement in median OS) at a 2-tailed significance level of 0.05 and an enrollment duration of approximately 52 months (13 subjects/month enrollment) over a total study duration of 64 months to obtain the required 514 events.

The OS endpoint will incorporate group sequential design by including 1 interim analysis and 1 final analysis using the O'Brien-Fleming boundaries as implemented by the Lan-DeMets alpha spending method. Subjects will be randomized in a 1:1 ratio to receive trabectedin + DOXIL combination therapy or DOXIL monotherapy.

## 2. ANALYSES PLANNED

### 2.1. General Analysis Definitions

#### 2.1.1. Definition of Cycle, Treatment Phase, Baseline

**Cycle:** The duration of cycles may not consistently be as the planned 21 days in the trabectedin + DOXIL Arm or 28 days in the DOXIL Arm, it will depend on the earliest date of the DOXIL/trabectedin doses given in the next cycle. If a subject experiences toxicity at the planned start of a cycle that leads to a delay in DOXIL/trabectedin administration, this new cycle will be delayed, and the previous cycle will be prolonged (without additional DOXIL or trabectedin treatment).

The start of the cycle is the date of the first administration of DOXIL or trabectedin in a cycle. The end of a cycle is the day before the first infusion of the immediate subsequent cycle recorded on the case report form (CRF).

The last cycle ends 3 weeks after the start of this cycle for the trabectedin + DOXIL Arm, and 4 weeks for the DOXIL Arm.

The assessments performed during the 'End-of-treatment visit' will be included in the last treated cycle for analysis.

All lab samples taken after the last treatment and up to 30 days after the last DOXIL/trabectedin infusion will be captured in the last cycle.

**End-of-treatment phase:** The end of the treatment phase is the date the last cycle ends, i.e., 3 weeks after the first trabectedin or DOXIL dosing in the last cycle for Arm A, or 4 weeks after the dose of DOXIL in the last cycle for Arm B.

YONDELIS®: Statistical Analysis Plan Study ET743-OVC-3006

**Follow-up phase:** Following termination of DOXIL/trabectedin treatment, subjects are followed every 8 weeks for survival for the first 2 years after randomization and every 3 months thereafter until death or the clinical cut-off date defined at the time when 514 deaths are observed, whichever is sooner. If disease progression has not occurred at treatment termination, then disease assessment should continue every 8 weeks until there is evidence of disease progression or death, or until the clinical data cut-off date, or until the start of first subsequent therapy for ovarian cancer, whichever is earlier. Disease assessment will also be done if necessary to confirm response or document disease progression.

**Relative day:** Assessments will be presented chronologically by cycle day or study day, which are defined in the following:

Cycle day = assessment date - date of first DOXIL or trabectedin infusion for the cycle + 1

Study day = assessment date - date of first DOXIL or trabectedin infusion in cycle 1 + 1

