### **2.2.5. Extent of Exposure**

#### **Cycle duration:**

Cycle duration (weeks) is defined as:

$[(\text{The earliest dosing date of trabectedin or DOXIL in the next cycle}) - (\text{the earliest dosing date of trabectedin or DOXIL in the current cycle})] / 7$

For the final cycle, cycle duration is equal to the pre-planned duration, ie, 3 weeks for the trabectedin + DOXIL arm and 4 weeks for the DOXIL arm.

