#### **Treatment duration:**

The treatment duration (weeks) is defined as:

$[(\text{The last cycle end date}) - (\text{the first cycle start date}) + 1] / 7$

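### Read literally, the SAP's treatment duration runs one day longer than the sum of its own cycle durations, so a fully dosed, on-schedule subject scores below 100% relative dose intensity

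*SAP*

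**What the plan says.** SAP 2.1.1 (Definition of Cycle, Treatment Phase, Baseline) has two conventions for a cycle's end date.

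- For a cycle followed by another: "The end of a cycle is the day before the first infusion of the immediate subsequent cycle".
- For the final one: "The last cycle ends 3 weeks after the start of this cycle for the trabectedin + DOXIL Arm", and 4 weeks after it in the DOXIL arm.

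The same section repeats the second rule when it defines the end of the treatment phase. There the date is 3 weeks after the first dosing of the last cycle in Arm A, or "4 weeks after the dose of DOXIL in the last cycle for Arm B".

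SAP 2.2.5 (Extent of Exposure) uses these dates. Cycle duration is the plain difference between consecutive cycle start dates, divided by 7. "For the final cycle, cycle duration is equal to the pre-planned duration", namely 3 weeks in the combination arm and 4 weeks in the DOXIL arm. Under the next heading, "The treatment duration (weeks) is defined as" introduces a formula that subtracts the first cycle's start date from the last cycle's end date, adds 1 and divides by 7.

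Dose intensity is cumulative dose over treatment duration. Relative dose intensity divides that by the planned value: trabectedin 1.1 mg/m² and DOXIL 30 mg/m² per 3 weeks in Arm A, DOXIL 50 mg/m² per 4 weeks in Arm B.

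**The concern.** Adding 1 to a date difference is correct when both dates lie inside the interval being counted. An end date on the day before the next infusion meets that condition. A date exactly 3 or 4 weeks after the last cycle's start does not: it is the day on which the next infusion would have been due. The last cycle is then counted as 22 or 29 days, although 2.2.5 says it lasts 3 or 4 weeks.

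Treatment duration is the denominator of dose intensity, so the extra day lowers dose intensity and relative dose intensity. A subject given every planned dose on time should score exactly 100%, and on this reading none would. The text also lets two programmers, one reading the end date literally and one inclusively, produce different exposure tables from the same SAP.

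**Working it through.** **Inputs.** Planned cycle length L is 21 days (Arm A) or 28 days (Arm B), from SAP 2.1.1. The end-date rules are from 2.1.1, and the formulas and planned dose intensities from 2.2.5. The documents do not report cycles received, so n is assumed to run from 1 to 12, with every dose full and on schedule.

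**The plan's own figure.** By the cycle-duration rule in 2.2.5, each on-schedule cycle lasts L days and the final one is set to L days. The sum over n cycles is L × n days. For n = 1 this is 21 days = 3 weeks (Arm A) or 28 days = 4 weeks (Arm B).

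**Treatment duration, read literally.**

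- Last cycle start = first start + L(n − 1).
- Last cycle end = last cycle start + L = first start + L × n.
- Treatment duration = L × n + 1 days.

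For n = 1 this gives 22 days = 3.143 weeks (Arm A) and 29 days = 4.143 weeks (Arm B). The stated 3 and 4 weeks are not reproduced. The excess is one day for every n.

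**Relative dose intensity (RDI).** With full doses, RDI = L × n / (L × n + 1) = 1 − 1/(planned days + 1).

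| Cycles | Arm A | Arm B |
|---|---|---|
| 1 | 21/22 = 95.5% | 28/29 = 96.6% |
| 2 | 42/43 = 97.7% | 56/57 = 98.2% |
| 4 | 84/85 = 98.8% | 112/113 = 99.1% |
| 5 | 105/106 = 99.1% | 140/141 = 99.3% |
| 6 | 126/127 = 99.2% | 168/169 = 99.4% |
| 12 | 252/253 = 99.6% | 336/337 = 99.7% |

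The shortfall falls below 1 percentage point from 5 cycles in Arm A and from 4 cycles in Arm B.

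In dose units after one cycle:

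- Arm A trabectedin: 1.1 × 21/22 = 1.05 mg/m² per 3 weeks.
- Arm A DOXIL: 30 × 21/22 = 28.64 mg/m² per 3 weeks.
- Arm B DOXIL: 50 × 28/29 = 48.28 mg/m² per 4 weeks.

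**Comparison between arms.** The shortfall is a function of total planned days.

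- Equal number of cycles: larger in Arm A (4.5 against 3.4 points at one cycle, 0.8 against 0.6 at six).
- Equal time: 84 days is 4 Arm A or 3 Arm B cycles, and RDI is 84/85 = 98.82% in both. 168 days is 8 or 6 cycles, and RDI is 168/169 = 99.41% in both.
- Longer time in Arm A: 6 Arm A cycles give 126/127 = 99.21%, and 4 Arm B cycles give 112/113 = 99.12%, so Arm B has the larger shortfall.

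**Check of the remedies.** If the last cycle ends at start + L − 1 and the + 1 stays, duration is (L × n − 1) + 1 = L × n days. If the end date stays and the + 1 goes, duration is L × n days. Either gives RDI = 100% for every n in both arms. Making both changes gives L × n − 1 days, which for one Arm A cycle is 20 days and RDI = 21/20 = 105%.

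**The case against.** The best defence is that the wording is loose rather than wrong. SAP 2.2.5 fixes the final cycle at its planned length, 2.1.1 numbers the infusion day as Day 1, and every other cycle ends the day before the next infusion. On that basis a 3-week last cycle runs from Day 1 to Day 21, its end date is start + 20, the + 1 is a correct inclusive count, and a fully dosed subject scores 100%. This may well be what was intended. It is not what the text says: 2.1.1 uses day-before wording for the other cycles and does not use it for the last one, and it repeats the 3- and 4-week rule when dating the end of the treatment phase.

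The second objection is size, and it stands. SAP 2.2.5 gives these variables descriptive statistics only. Treatment-emergent events (SAP 2.2.9.1) are dated from the last dose plus 30 days, so they do not move. Protocol Section 6 allows a +2-day dosing window, and the SAP's delay table starts at 5 days. Using the full window at each of the five later cycles of a six-cycle Arm A course would by itself bring RDI to 126/136 = 92.6%. The extra day takes it to 126/137 = 92.0%.

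A reader might infer that the extra day understates dose intensity more in Arm A and so distorts the comparison between arms. The documents do not support that as a general statement. It holds at an equal number of cycles, disappears at equal time on treatment, and reverses if Arm A is treated longer. No cycle counts by arm are given, so the direction cannot be established.

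**Conclusion.** The point holds on the literal reading of SAP 2.1.1. Followed as written, the definitions make treatment duration exceed the sum of the SAP's cycle durations by one day, and they contradict the final-cycle duration stated in 2.2.5. The loss in relative dose intensity for a fully dosed, on-schedule subject is 1/(planned days + 1): a few percentage points for someone who stops after one or two cycles, and under one point from the fifth cycle (Arm A) or the fourth (Arm B).

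This rests on taking 3 or 4 weeks after the start as start + 21 or start + 28 days, and on assumed cycle counts. If the inclusive meaning is programmed, the error vanishes, but the text still needs to say so.

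The effect is confined to the summaries of treatment duration, dose intensity and relative dose intensity. Cumulative dose, number of cycles, overall survival and all hypothesis tests are unaffected. No differential effect between arms is established. This is a minor correction.

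**What to change.** Make one of these changes, not both.

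1. Drop the + 1 from the treatment-duration formula in SAP 2.2.5 and leave the end dates alone. The formula then matches the plain date difference that 2.2.5 already uses for cycle duration.
2. Keep the + 1 and define the last cycle's end as start + 20 days (Arm A) or start + 27 days (Arm B). This must be changed in both places in 2.1.1, the last-cycle rule and the end-of-treatment-phase definition, or the two will disagree.

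The first is the smaller edit, because the second also moves the end of the treatment phase by a day. The cost is one line of SAP text (two for the second option) and one line of code. A useful check is that a subject with full, on-time dosing returns exactly 3n or 4n weeks and 100%. The change concerns an analysis definition only and does not touch dosing.

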## 8. PRESTUDY AND CONCOMITANT THERAPY

Prestudy therapies administered up to 30 days before first dose of study drug must be recorded at screening.

Concomitant therapies must be recorded throughout the study beginning from the time the ICF is signed to 30 days after the last dose of study drug or until 18 January 2018, whichever occurs first. Concomitant therapies should be recorded beyond 30 days after the last dose of study drug only in conjunction with serious adverse events that meet the criteria outlined in Section 12.3.2, Serious Adverse Events.

All therapies (prescription or over-the-counter medications, including vaccines, vitamins, herbal supplements; non-pharmacologic therapies such as electrical stimulation, acupuncture, special diets, exercise regimens) different from the study drug must be recorded in the CRF. Recorded information will include a description of the type of the drug, treatment period, dosing regimen, route of administration, and its indication. Modification of an effective preexisting therapy should not be made for the explicit purpose of entering a subject into the study.

Premedication with IV dexamethasone (or an equivalent IV corticosteroid) is required for subjects in the trabectedin group. The use of IV dexamethasone (or an equivalent IV corticosteroid) for this purpose is not considered concomitant therapy and will be documented as a required pretreatment medication on the study drug administration section of the CRF. Additional corticosteroid administration is allowed for antiemetic purposes. The use of IV dexamethasone (or an equivalent IV corticosteroid) for reasons other than the required pretreatment of subjects in the trabectedin group should be documented in the concomitant therapy section of the CRF, and the associated indication should be recorded as an adverse event, if appropriate.

Any new condition or a worsening of an existing condition that requires the use of new or altered doses of concomitant therapies must be documented on the adverse events section of the CRF. Subjects may receive supportive care while receiving study drug, including transfusions, hematopoietic growth factors, antibiotics, analgesics, and antidiarrheal agents. Megestrol acetate may be used only for appetite stimulation.

Concomitant medications or therapies should be documented in the CRF. This includes:

- Antiinfective medications (eg, antibiotics, antifungals, antivirals)
- Hematopoietic cytokines

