#### **Adverse Events**

The verbatim terms used in the CRF by investigators to identify adverse events will be coded using the Medical Dictionary for Regulatory Activities (MedDRA) and will be graded according to the NCI-CTCAE, Version 4.0. All reported adverse events with onset during the treatment phase (ie, those events that occur or worsen on or after the first dose of study drug up through 30 days after the last dose of study drug) will be included in the analysis. Adverse events will be summarized by MedDRA system organ class and preferred term. For each adverse event, the percentage of subjects who experience at least 1 occurrence of the given event will be summarized overall and by treatment group. Serious adverse events and deaths will be listed. All adverse events resulting in discontinuation of study treatment, dose modification, the interruption of dosing, or a delay in treatment with the study drug will be listed and summarized by preferred term.

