### **2.2.7. Concomitant Medications**

Concomitant therapies will be categorized per coded term. The number of subjects receiving each type of therapy during the treatment phase will be tabulated in 2 separate tables: a frequency tabulation of the different therapies that started pre-trial, and a frequency tabulation of the different therapies that started during the trial. The accompanying listing will contain all concomitant therapies.

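### The concomitant-therapy table stops 21 days after the last-cycle dose in Arm A and 28 days in Arm B, although therapy is recorded to 30 days in both arms

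*SAP*

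**What the plan says.** SAP 2.1.1 fixes the end of the treatment phase as the date the last cycle ends: "3 weeks after the first trabectedin or DOXIL dosing in the last cycle for Arm A, or 4 weeks after the dose of DOXIL" (the latter for Arm B).

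SAP 2.2.7 uses that term for the therapy summary: "The number of subjects receiving each type of therapy during the treatment phase will be tabulated in 2 separate tables". One table is for therapies begun before the trial and one for those begun during it. No longer window is given for either. The same section adds: "The accompanying listing will contain all concomitant therapies".

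Protocol Section 8 sets the recording period, without distinction by arm: "beginning from the time the ICF is signed to 30 days after the last dose of study drug or until 18 January 2018", whichever comes first. All such therapies "different from the study drug must be recorded in the CRF". The footnotes to both arms' Time and Events Schedules and the treatment termination visit text in Protocol 9.1.4 give the same 30 days.

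Other safety summaries use 30 days in both arms: treatment-emergent adverse events (SAP 2.2.9.1), laboratory samples (SAP 2.1.1) and deaths (SAP 2.2.9.4). In Protocol 11.7, under Adverse Events, the treatment phase covers events "on or after the first dose of study drug up through 30 days after the last dose of study drug".

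**The concern.** The cut-off for one descriptive table depends on the assigned arm, while the data behind it are recorded over the same period in both arms. The shorter window is in the arm where more supportive care is expected. Protocol Section 8 strongly recommends prophylactic G-CSF for Arm A only. In the earlier Phase 3 study summarised in Protocol 1.2.2, Grade 3 or 4 neutropenia was 63% with the combination against 23% with DOXIL alone, and neutropenic fever 8% against 2%.

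The days lost in Arm A are not idle ones. Protocol 6.1 allows a dosing delay of up to 3 weeks for toxicity. If the subject resumes, SAP 2.1.1 prolongs the previous cycle and care given during the delay is counted. If she stops, the last cycle closes at its planned length and later care is not counted. The tables can also disagree: an infection starting on day 25 after the last dose in Arm A enters the adverse-event table, but an antibiotic type first used for it does not enter the therapy table. In Arm B both would be counted.

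At stake is a fair side-by-side description of supportive care in an open-label trial whose stopping recommendation cited higher toxicity in Arm A.

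**Working it through.** The plan gives no figure of its own on this point, so there is none to reproduce. The check is day arithmetic, followed by an illustration resting on an assumed rate.

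**Inputs**
- End of treatment phase (SAP 2.1.1): 3 weeks in Arm A, 4 weeks in Arm B, counted from the last-cycle dose.
- Table window (SAP 2.2.7): the treatment phase, with no extension.
- Recording window (Protocol Section 8): 30 days after the last dose in both arms, or 18 January 2018 if earlier.

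**Days recorded but not tabulated after the last dose**

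| | Arm A | Arm B |
|---|---|---|
| Tabulated | 3 × 7 = 21 | 4 × 7 = 28 |
| Recorded | 30 | 30 |
| Omitted | 30 − 21 = 9 | 30 − 28 = 2 |
| Share of the 30-day tail | 9/30 = 30% | 2/30 = 6.7% |

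These shares refer only to the tail after the last dose. As a share of the whole recorded period from first dose, assuming six undelayed cycles:
- Arm A: 5 × 21 + 30 = 135 days; 9/135 = 6.7% omitted.
- Arm B: 5 × 28 + 30 = 170 days; 2/170 = 1.2% omitted.

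**What is lost.** The table counts subjects ever receiving each type of therapy. A subject is missed for a type only if her first use falls in the omitted days.

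**Illustration.** The documents give no rate of first use after the last dose. Assume the same 30-day risk r in both arms, with a constant daily rate λ = −ln(1 − r)/30, among subjects who had not used the type by the last dose. Then:
- missed in Arm A = exp(−21λ) − exp(−30λ)
- missed in Arm B = exp(−28λ) − exp(−30λ)

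| Assumed r | Missed per 100, Arm A | Missed per 100, Arm B | Difference |
|---|---|---|---|
| 5% | 1.5 | 0.3 | 1.1 |
| 10% | 2.9 | 0.6 | 2.3 |
| 20% | 5.5 | 1.2 | 4.3 |
| 30% | 7.9 | 1.7 | 6.2 |

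(Differences are taken before rounding.) The denominator is non-users at the last dose, not all randomized subjects.

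**Direction.** The loss would be equal only if daily first use in the omitted days were about 9/2 = 4.5 times higher in Arm B.

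**After the fix.** With one 30-day window the omitted days become 0 and 0.

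**The case against.** **The text may not require the narrow window.** The second table is for therapies begun during the trial, a phrase with no 21- or 28-day limit, and SAP 2.1.1 places end-of-treatment visit assessments in the last treated cycle. Neither settles the matter. The begun-during-the-trial wording divides output already limited to the treatment phase, and the visit sentence concerns assessments and does not move the dated end of that phase. SAP 2.1.1 extends laboratory samples to 30 days expressly and says nothing similar for therapies.

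**Tabulating a subset of what is recorded contradicts nothing.** This stands as far as it goes. Protocol Section 8 is a recording rule, and Protocol 11.7 specifies no concomitant-therapy analysis. A reader might infer that the protocol defines the treatment phase as 30 days for every purpose; it does so only for adverse events. Nor can a conflict with the case report form be asserted, since the form is not among the documents. The problem is the unequal cut-off between arms, not a breach of the protocol.

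**The effect is small.** This also stands. A reader might take 30% against 7% to mean that nearly a third of Arm A's supportive care is lost. Those are shares of the tail alone, and earlier users still count. In particular, a subject given prophylactic G-CSF in any treated cycle is already in the table, so the documents do not support a claim that G-CSF use as a whole is materially under-counted.

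**Nothing rests on the table.** It is descriptive, carries no test, and concomitant therapy is not among the safety parameters named in Protocol 11.7. The listing is complete, though a listing does not correct a frequency comparison between arms.

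**Conclusion.** The point holds as a modest inconsistency in one descriptive table. As written, SAP 2.1.1 and 2.2.7 together omit about 9 recorded days after the last dose in Arm A and about 2 in Arm B. First use of a therapy type is therefore under-counted somewhat more in Arm A, unless daily first use in the omitted days is about 4.5 times higher in Arm B.

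The day counts assume that the last-cycle dose is the last dose and that the full 30 days were recorded. For subjects still on treatment at Amendment 6, the 18 January 2018 cut-off can shorten the recorded period in either arm. The number of subjects affected cannot be derived from the documents; the figures per 100 depend wholly on the assumed risks of 5% to 30%.

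A reader might go further and infer that the toxicity comparison or the trial's conclusions are biased in favour of the combination. The documents do not support that. Adverse events, laboratory samples and deaths already use 30 days in both arms, and OS, PFS and ORR do not depend on this window.

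**What to change.** In SAP 2.2.7 only, state that concomitant therapy received from the first dose through 30 days after the last DOXIL or trabectedin dose will be tabulated in both arms, truncated at 18 January 2018. Keep the split into two tables and the full listing.

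Leave the end-of-treatment-phase definition in SAP 2.1.1 alone. It is tied to the last-cycle end date, which SAP 2.2.5 uses for treatment duration and hence dose intensity. Changing it would either break that link or alter the exposure results.

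The cost is one sentence and one date condition in the table program. The protocol already requires the data, and no clinical rule changes.
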